### **Maximum duration of Platelet and RBC transfusion independence**

Transfusion independence duration will be defined as the period from the next day of transfusion to the day before the next transfusion. Maximum duration of platelet and RBC transfusion independence will be summarized separately. The proportion of subjects with platelet and/or RBC transfusion independence will be summarized separately.

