2.1.1 Data included in the analysis

The analysis cut-off date for the primary analysis of study data will be established after all enrolled patients have completed 26 weeks of treatment or have discontinued prior to Week 26. All statistical analyses will be performed using all data collected in the database up to the data cutoff date. All data with an assessment date or event start date (e.g. vital sign assessment date or start date of an adverse event) prior to or on the cut-off date will be included in the analysis. Any data collected beyond the cut-off date will not be included in the analysis and will not be used for any derivations.

All events with start date before or on the cut-off date and end date after the cut-off date will be reported as 'ongoing'. The same rule will be applied to events starting before or on the cut-off date and not having documented end date. This approach applies, in particular, to adverse event, concomitant medication reports and exposure to eltrombopag. For these events, the end date will not be imputed and therefore will not appear in the listings.

The analysis cutoff date for the updated analysis and final analysis of study data will be established after all patients have completed Week 52 or discontinued prior to Week 52 and at the end of the study respectively.

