For subjects receiving platelet transfusion at baseline, the frequency and the amount of platelets transfusion in each period (Baseline: 4 weeks before Day 1; Week 13, 26, 52: 4 weeks before each visit day) will be summarized. The same analysis applies to RBC transfusion (period will be extended to 8 weeks). The amount of transfusion will be defined as the sum of transfusion multiplied by the volume of transfusion.

The analysis for frequency and amount of transfusion will not be reproduced for final CSR.

Proportion of subjects with transfusion decrease

Subjects with platelet transfusion decrease is defined as subjects with transfusion decrease or transfusion free in each period (Week 13, 26, 52: 4 weeks before each visit day) compared to baseline (Baseline: 4 weeks before Day 1). 50% platelet transfusion reduction is defined as subjects with transfusion decrease of amount (units) at least 50% compared to baseline. The same analysis applies to RBC transfusion (period will be extended to 8 weeks). This analysis will be performed for the subgroup of subjects with baseline transfusion dependent.

The analysis for proportion of subjects with transfusion decrease will not be reproduced for final CSR.

Maximum duration of Platelet and RBC transfusion independence

Transfusion independence duration will be defined as the period from the next day of transfusion to the day before the next transfusion. Maximum duration of platelet and RBC transfusion independence for each subject will be picked for analysis.

Post-baseline transfusion independence will be achieved if subjects who are transfusion dependent at baseline become transfusion free for a period of at least 28 (platelets) or 56 days (RBCs). The time period for assessment of transfusion independence will be at any time during the treatment period. Baseline platelet and RBC transfusion dependence is defined as subjects receiving at least one platelet or RBC transfusion in the 4 weeks and 8 weeks, respectively, prior to the first dose of eltrombopag.

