Maximum duration of Platelet and RBC transfusion independence

Maximum duration of platelet and RBC transfusion independence will be summarized by descriptive statistics including mean, SD, median, 25th and 75th percentiles, minimum, and maximum separately.

The summary of shift baseline for platelet transfusion independence and RBC transfusion independence will be presented.

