5.1.2 AE, ConMeds and safety assessment date imputation

Table 5-1 Imputation of start dates (AE, CM) and assessments (LB, EG, VS)

Missing Element	Rule
day, month, and year	
• No imputation will be done for completely missing dates
day, month	
• If available year = year of study treatment start date then
◦ If stop date contains a full date and stop date is earlier than study treatment start date then set start date = 01JanYYYY
◦ Else set start date = study treatment start date.• If available year > year of study treatment start date then 01JanYYYY• If available year < year of study treatment start date then 01JulYYYY
day	
• If available month and year = month and year of study treatment start date then
◦ If stop date contains a full date and stop date is earlier than study treatment start date then set start date= 01MONYYYY.
◦ Else set start date = study treatment start date.• If available month and year > month and year of study treatment start date then 01MONYYYY• If available month and year < month year of study treatment start date then 15MONYYYY

Table 5-2 Imputation of end dates (AE, CM)

Missing Element	Rule (*=last treatment date plus 30 days not > (death date, cut-off date, withdrawal of consent date))
day, month, and year	
• Completely missing end dates (incl. ongoing events) will be imputed by the end date of the on-treatment period*
day, month	
• If partial end date contains year only, set end date = earliest of 31DecYYYY or end date of the on-treatment period *
day	
• If partial end date contains month and year, set end date = earliest of last day of the month or end date of the on-treatment period*

Any AEs and ConMeds with partial/missing dates will be displayed as such in the data listings.

Any AEs and ConMeds which are continuing as per data cut-off will be shown as 'ongoing' rather than the end date provided.

The above imputations are only used for analyses of time to and duration of AEs and concomitant medications.

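### Maximum duration of transfusion independence has no end rule for a spell that no later transfusion closes, and no censoring of such spells

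*SAP*

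**What the plan says.** Protocol 12.5.1, under the heading on maximum duration of platelet and RBC transfusion independence, states: "Transfusion independence duration will be defined as the period from the next day of transfusion to the day before the next transfusion". SAP 2.7.1 repeats the definition, "the period from the next day of transfusion to the day before the next transfusion", and takes each subject's maximum. SAP 2.7.2 adds the method: "Maximum duration of platelet and RBC transfusion independence will be summarized by descriptive statistics", namely mean, SD, median, quartiles, minimum and maximum.

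Under the same heading, SAP 2.7.1 defines a separate yes/no status for subjects who were transfusion dependent at baseline. They count as independent if they "become transfusion free for a period of at least 28 (platelets) or 56 days (RBCs"), and on timing: "The time period for assessment of transfusion independence will be at any time during the treatment period". That status needs no closing transfusion.

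The opening of SAP 2.7.1 names three secondary efficacy analyses for the final CSR: changes in counts, duration of hematological response, and this one.

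**The concern.** The definition measures a gap between two transfusions. The subjects for whom the endpoint matters most are those whose transfusions stop, and their last gap never closes. Applied as written, the table keeps only the gaps from the time when they were still being transfused. A subject never transfused on study contributes no value, and the SAP does not say whether that is missing, zero or the whole observation time.

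A sensible programmer would probably close the open gap somewhere. Last dose, last dose plus 30 days, last visit and data cut-off are all defensible and give different answers. None of them turns the value into a completed duration: it is the time observed so far, and it grows with follow-up. A plain mean or median treats it as finished. Follow-up is longest at the final CSR, so the choice matters most there.

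**Working it through.** **Does any rule in the documents close or censor the spell?**

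- SAP 2.7.3 gives missing-data or censoring rules for response at Weeks 13 and 52, time to response, and duration of response. It has none for transfusion independence. Duration of response is censored at the last response assessment for subjects still responding.
- SAP 2.1.1 excludes data after the cut-off and reports open records as ongoing: "For these events, the end date will not be imputed and therefore will not appear in the listings". Even if this covers a transfusion-free spell, it supplies no end date and so no length.
- SAP 2.1.3 defines the on-treatment period and the last administration date. It does not link either to this duration.
- SAP 5.1.2, Table 5-2, imputes missing end dates up to "last treatment date plus 30 days not > (death date, cut-off date, withdrawal of consent date"), but its note limits the use: "The above imputations are only used for analyses of time to and duration of AEs and concomitant medications". If transfusions are treated as concomitant therapy, the table would impute the end of a transfusion record, not the end of the time without one.
- The any-time wording in SAP 2.7.1 bounds the search for the 28- or 56-day status. It does not say how long an open spell lasts.

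No passage closes the spell. The plan states no figure for this endpoint, so there is none to reproduce.

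**Illustration 1: one subject (assumed dates).** Transfusions on Days 5, 12, 19, 26 and 40, then none.

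Closed spell = later day − earlier day − 1:
- 12 − 5 − 1 = 6; 19 − 12 − 1 = 6; 26 − 19 − 1 = 6; 40 − 26 − 1 = 13.
- Maximum as written: 13 days.

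Open spell, counted through Day E = E − 40:

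| Closing day E | Length (days) |
|---|---|
| 182 (Week 26) | 142 |
| 364 (Week 52) | 324 |
| 394 (Day 364 + 30) | 354 |
| 728 (Week 104) | 688 |

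If dependent at baseline, this subject meets the platelet status rule of at least 28 days, yet has a maximum duration of 13 days in the same section of the report.

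**Illustration 2: 20 subjects (assumed pattern).** All are transfused every 14 days, so each closed spell is 14 − 1 = 13 days. Eight have their last transfusion on Day 84; 12 continue. Eight is 40% of 20, with the planning rate borrowed only to obtain a count.

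Open spell: 364 − 84 = 280 days, or 728 − 84 = 644 days.

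| Rule | Mean | Median | 75th percentile |
|---|---|---|---|
| Closed spells only | 13 | 13 | 13 |
| Open spells counted to Day 364 | (8×280 + 12×13)/20 = 119.8 | 13 | 280 |
| Open spells counted to Day 728 | (8×644 + 12×13)/20 = 265.4 | 13 | 644 |

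The last two rows contain the same transfusions; only follow-up differs. The median stays at 13 because 12 of the 20 values are 13. It would move only if at least half the subjects had open spells; with 12 of 20 it would be 280 or 644.

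**Sensitivity to the regular pattern.** With gamma-distributed intervals of mean 14 days and coefficient of variation 0.25, 0.5 or 1.0, the simulated mean of the longest closed spell by Day 182 is about 19, 26 or 40 days. The literal figure is then less extreme than 13, but still far below the open spells above.

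**The case against.** The strongest reply is that the literal reading is implausible. The adjoining paragraph calls a subject independent without any closing transfusion, SAP 2.1.3 defines the treatment period, and SAP 2.1.1 bars data after cut-off. On that view the bounds exist and one sentence applying them is missing. This stands in part: dropping the last spell would sit badly with the status rule. But the documents do not choose among the possible bounds, and choosing one would still leave the values uncensored in a plain mean.

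The illustrations are also open to fair criticism. The 40% is response in any of three lineages, not the rate of becoming free of platelet or RBC transfusion. Some subjects will be transfusion independent at baseline. Perfectly regular transfusion is unrealistic. All of this stands, so the figures show direction and dependence on the end rule, not an expected size.

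A third objection concerns the obvious remedy of ending open spells at last dose plus 30 days. SAP 2.1.3 takes the last nonzero dose, and the protocol provides for treatment to be interrupted after a sustained good response (Section 3, Table 6-4). Such an end date could truncate the best responders, although transfusions are recorded to completion of follow-up (Protocol 6.2.1). This stands, and the fix below avoids that date.

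A reader might also infer that the baseline-shift table is at fault, because it sets one fixed baseline window against the best spell at any time on treatment. The documents do not support that as a defect. The any-time rule is stated openly, and the 28- and 56-day lengths match the 4- and 8-week baseline windows. Comparisons in equal windows before Weeks 13, 26 and 52 are already specified in SAP 2.7.1 and 2.7.2, although they are not repeated for the final CSR. Any inflation depends wholly on transfusion patterns that the documents do not give.

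**Conclusion.** The gap is real. Neither document says when an open transfusion-free spell ends, and neither treats it as censored. Applied as written, the rule understates the outcome of subjects who stop needing transfusions and leaves never-transfused subjects without a value. Closed informally, the summary depends on an unstated date and on length of follow-up.

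The size cannot be taken from the documents. Under the assumed dates, one subject's value runs from 13 to 688 days and a 20-subject mean from 13 to 265.4 days, depending only on the end rule and follow-up.

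It would go too far to infer that the reported table will be wrong, since a programmer may close the spells reasonably, or that the trial's efficacy conclusion is at risk. The analysis is secondary and descriptive, and the primary endpoint does not use it. The change is still worth making, because this is one of only three secondary efficacy analyses carried into the final CSR and the correction is cheap.

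**What to change.** Add to SAP 2.7.1 and 2.7.3:

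1. Include open spells when picking each subject's maximum.
2. Start the first spell at Day 1 if there is no earlier on-study transfusion. This also gives never-transfused subjects a value.
3. End an open spell at the last date through which transfusions were recorded for that subject (completion of follow-up or last contact), not later than death, withdrawal of consent or data cut-off. Do not use last dose plus 30 days.
4. Flag a maximum that comes from an open spell as ongoing (censored), and report how many there are for platelets and for RBC.
5. Either estimate the distribution by Kaplan-Meier, as for duration of response, or keep the descriptive statistics and label the mean and median as lower bounds.

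The cost is a few sentences in the SAP and minor reprogramming. No new data are needed, because Protocol 6.2.1 already requires transfusions to be recorded to completion of follow-up. The drawback is that some durations must be read as incomplete.

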2.7.2 Statistical hypothesis, model, and method of analysis

Hematological Response at Week 13 and Week 52

The number and percentage of subjects who meet the hematological response criteria (at Week 13 and Week 52 respectively) will be presented and exact 90% confidence interval will be reported. And the number and percentage of assessment item for the hematological response criteria and for the detailed hematological response criteria will be presented.

The derived response by programming at week 13 and Week 52 will also be summarized as above.

Changes in platelet count, hemoglobin and neutrophil count

Values and changes in platelet count (in the absence of platelet transfusion), hemoglobin (in the absence of RBC transfusion) and neutrophil count (in the absence of G-CSF) will be summarized at each visit. Descriptive statistics including mean, SD, median, 25th and 75th percentiles, minimum, and maximum will be summarized for the changes.

Median and interquartile range will be plotted.

Time to hematological response

The distribution function of time to hematologic response will be estimated using the Kaplan-Meier method and will be plotted. The median time to hematologic response along with 90% CIs will be presented. If a subject does not meet hematological response before or at the cutoff date, censoring will be performed using the date of the last assessment.

Duration of hematological response

The distribution function of duration of hematologic response will be estimated using the Kaplan-Meier method and will be plotted. If the number of relapses or deaths allows, the median time to hematologic response along with 90% CIs will be presented.

Relapse-free probability will be estimated using the Kaplan-Meier method at 3 months, 6 months, 9 monthes, one year, and yearly after as well.

Frequency and amount of transfusion

The frequency and the amount of platelets transfusion in each period (Baseline: 4 weeks before Day 1; Week 13, 26, 52: 4 weeks before each visit day) will be summarized by descriptive statistics including mean, SD, median, 25th and 75th percentiles, minimum, and maximum.

Proportion of subjects with transfusion decrease

The number and percentage of subjects with platelet or RBC transfusion decrease or transfusion-free in each period will be presented.

In addition, the number and percentage of subjects with 50% platelet or RBC transfusion reduction in each period will be presented.

Maximum duration of Platelet and RBC transfusion independence

Maximum duration of platelet and RBC transfusion independence will be summarized by descriptive statistics including mean, SD, median, 25th and 75th percentiles, minimum, and maximum separately.

The summary of shift baseline for platelet transfusion independence and RBC transfusion independence will be presented.

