**Table 6-3 Criteria for dose adjustment of eltrombopag between Week 1 and Week 26**

Standards of platelet count	Dose adjustment
At 2 weeks or more of administration, the platelet count is $< 50 \times 10^9/L$ , or the amount required for platelet transfusion does not decrease.	Titrate the dose by 25 mg each every 2 weeks up to 150 mg/day.
At 2 weeks or more of administration, the platelet count is $\geq 50 \times 10^9/L$ , and is $\leq 100 \times 10^9/L$ .	Maintain the dose.
The platelet count is $> 100 \times 10^9/L$ under no blood transfusion	Reduce the dose by 25 mg each every 2 weeks until the platelet count can be maintained at $100 \times 10^9/L$ or lower.
The platelet count is $> 200 \times 10^9/L$ under no blood transfusion	Interrupt the drug until the platelet count becomes $< 50 \times 10^9/L$ . Thereafter, restart administration at the dose 25 mg lower (The restarting dose is 25 mg/day if the dose at interruption was 25 mg/day).

If dose has increased to 150 mg/day at Week 12, the subject would maintain the maximum dose as 150 mg/day from Week 13 to Week 26. When dose decrease under 25 mg/day is needed, eltrombopag treatment should be interrupted until the platelet count becomes less than  $50 \times 10^9/L$ .

The criteria for dose adjustment of this drug after Week 26 are shown in [Table 6-4](#).

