**Table 8-1 Assessment Schedule**

Visit Name	Screening	Treatment							End of Study	
		Day 1	Week 1/2/3	Week 4	Week 5 to 51 (Every 2 weeks until stabilization of dose; every 4 weeks, after stabilization of dose) 	Week 13	Week 26/52	Extension part (Every 2 weeks until stabilization of dose; every 4 weeks after stabilization of dose) 	End of treatment	Follow-up (30 days after treatment discontinuation)
Days	-30 to -1	1 to 1	8 to 22	29 to 29	36 to 358	92	183 to 365	After Week 52	EOT	after EOT
Informed consent	X									
Demography	X									
Medical history/current medical conditions	X									
Characteristics of SAA	X									
Inclusion / Exclusion criteria	X									
Supportive therapy	X	X	X	X	X	X	X	X	X	X
Concomitant medications	X	X	X	X	X	X	X	X	X	X
Physical Examination	S	S	S	S	S	S	S	S	S	S
Vital Signs	X	X		X	Once a month	X	X	Once a month	X	X
Height	X									
Body Weight	X						X		X	
Standard 12 lead ECG	X						X	Once in 6 months (Example: Weeks 78, 104...)	X	
Adverse Events	X	X	X	X	X	X	X	X	X	X
Peripheral blood smear	X	X	X	X	X	X	X	X	X	X
Bone marrow aspiration (iliac crest) and cytogenetic analysis	Within 3 months of Day 1					X	X	Once in 6 months (Example: Weeks 78, 104...)	Not necessary if conducted within 6 months.	

Period	Screening	Treatment								End of Study	
Visit Name	Screening	Day 1	Week 1/2/3	Week 4	Week 5 to 51 (Every 2 weeks until stabilization of dose; every 4 weeks, after stabilization of dose) 	Week 13	Week 26/52	Extension part (Every 2 weeks until stabilization of dose; every 4 weeks after stabilization of dose) 	End of treatment	Follow-up (30 days after treatment discontinuation)	
Days	-30 to -1	1 to 1	8 to 22	29 to 29	36 to 358	92	183 to 365	After Week 52	EOT	after EOT	
assessment											
Evaluation of clonal evolution to AML and MDS	X	When clinically indicated.									
PK blood sampling		Intensive PK in 12 subjects (pre-dose, 1, 2, 4, 6, 8, and 24 h post-dose) on day 14 after initial dose; Sparse PK in all subjects: Pre-dose on day 15 after initial dose and pre-dose on day 15 after each new dose has started (dose escalation only)									
Prescription of eltrombopag		Eltrombopag will be distributed every 2 weeks or every 4 weeks after stabilization of dose according to Section 6.5									
Treatment compliance			S	S	S	S	S	S	S		
Disposition	X									X	X

X Assessment to be recorded in the clinical database or received electronically from a vendor

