S Assessment to be recorded in the source documentation only

 "Until stabilization of dose" means that the dose is not changed for at least 4 weeks. If the dose is changed at visiting every 4 weeks, the subject should visit hospital since the next visit until stabilization of dose.

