3. ***post-treatment period***: starting at day 30+1 after last administration of study treatment.

Safety summaries (tables, figures) include only data from the on-treatment period with the exception of baseline data which will also be summarized where appropriate (e.g. change from baseline summaries). In addition, a separate summary for death including on treatment and post treatment deaths will be provided. In particular, summary tables for adverse events (AEs) will summarize only on-treatment events, with a start date during the on-treatment period (***treatment-emergent*** AEs).

However, all safety data (including those from the post-treatment period) will be listed and those collected during the pre-treatment and post-treatment period will be flagged.

Windows for multiple assessments

In order to summarize hematological response collected over time (including unscheduled visits), the assessments will be time slotted. The following general rule will be applied in creating the assessment windows: If more than one assessment is done within the same time window, the assessment performed closest to the target date will be used. If 2 assessments within a time window are equidistant from the target date, then the earlier of the 2 assessments will be used. Data from all assessments (scheduled and unscheduled), including multiple assessments, will be listed.

Table 2-1 Time windows for hematological response

Assessment	Target day of assessment	Time Interval
Baseline	On or before Study Day 1	≤ Day 1
Week 13	Week 13 ± 3 days	Study Day 77 – 105 (i.e. 11 to 15 weeks)
Week 26	Week 26 ± 3 days	Study Day 168 – 196 (i.e. 24 to 28 weeks)
Week 52	Week 52 ± 3 days	Study Day 336 – 392 (i.e. 48 to 56 weeks)

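### By-visit count summaries between about Week 6 and Week 24 can compare different subjects at alternate visits, because visit frequency follows dose stability and hence platelet response

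*SAP*

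**What the plan says.** **Analysis.** Changes in platelets, hemoglobin and neutrophils are a secondary efficacy endpoint. SAP 2.7.2 says that platelet count (without transfusion), "hemoglobin (in the absence of RBC transfusion) and neutrophil count (in the absence of G-CSF) will be summarized at each visit" and that "Median and interquartile range will be plotted". SAP 2.7.1 lists this analysis among those to be generated for the final CSR.

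**Visits.** Weeks 1 to 4, 13, 26 and 52 are scheduled for every subject on study. For the other weeks from 5 to 51, Protocol Table 8-1 sets the interval as "Every 2 weeks until stabilization of dose; every 4 weeks, after stabilization of dose". Its footnote says that stabilization "means that the dose is not changed for at least 4 weeks".

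**Dose.** Up to Week 26, Protocol Table 6-3 links the dose to platelets. Below 50 x 10^9/L, or if platelet transfusion need does not decrease, the rule is "Titrate the dose by 25 mg each every 2 weeks up to 150 mg/day". From 50 to 100 x 10^9/L it is "Maintain the dose".

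**Windows.** SAP 2.1.3 begins its windowing rule "In order to summarize hematological response collected over time (including unscheduled visits), the assessments will be time slotted". Table 2-1 then gives windows for response only, at baseline and Weeks 13, 26 and 52. SAP 2.8.3 mentions time windows for safety laboratory boxplots but does not define them.

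**The concern.** Together, the dosing and visit rules let platelet response decide when a subject is next seen. A subject whose platelets reach 50 x 10^9/L early stops escalating and moves to 4-weekly visits. A subject who stays below 50 keeps 2-weekly visits until the dose reaches its ceiling and has been stable for 4 weeks. The two can then fall on different alternate weeks.

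A summary at each nominal visit would then describe one set of subjects one fortnight and another set the next. The change in who attends is related to the outcome being plotted. A reader of the CSR could take the resulting steps for onset, loss of effect or a dose effect. This can happen with everyone on treatment and every scheduled value present, so it is separate from dropout and from the transfusion and G-CSF exclusions.

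**Working it through.** **1. The plan's own figure.** The documents give no figure for the by-visit summaries. The only sizing figure is the 90% exact interval for 8/20 responders (SAP 3.1). It reproduces as (21.7%, 60.6%), and nothing below depends on it.

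**2. Are counts taken at every visit?** The hematology row of Table 8-1 is not in the text available to me. I infer that they are: the peripheral smear is marked in every visit column, and Protocol 8.4.4 puts hematology on the same day as the smear.

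**3. Calendar.** Apply Tables 6-3 and 8-1 without interruption. The dose starts at 25 mg and rises 25 mg every 2 weeks, the subject is stable 4 weeks after the last change, and the 4-week clock runs from that date. Visits after Week 4 (Weeks 13 and 26 omitted, since all attend):

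| Last change | Dose (mg) | Weeks attended |
|---|---|---|
| Day 1 | 25 | 8, 12, 16, 20, 24 |
| Week 2 | 50 | 6, 10, 14, 18, 22 |
| Week 4 | 75 | 6, 8, 12, 16, 20, 24 |
| Week 6 | 100 | 6, 8, 10, 14, 18, 22 |
| Week 8 | 125 | 6, 8, 10, 12, 16, 20, 24 |
| Week 10 | 150 | 6, 8, 10, 12, 14, 18, 22 |

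On this calendar, fully titrated subjects attend Weeks 14, 18 and 22, and Weeks 16, 20 and 24 hold only subjects who stabilised earlier.

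**4. Illustration (assumed values).** Take 20 subjects. Twelve reach 150 mg with no change in platelets. Eight gain 45 x 10^9/L, two each stabilising at 50, 75, 100 and 125 mg. The all-subject mean change is 8 x 45 / 20 = +18 and the median is 0.

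- Individual clocks, Weeks 18 and 22: n = 12 + 2 + 2 = 16; mean (12 x 0 + 4 x 45)/16 = +11.25; median 0.
- Individual clocks, Week 20: n = 2 + 2 = 4; mean and median +45.
- Common grid (Weeks 8, 12, 16, 20, 24): Weeks 12 and 16 have n = 20 and mean +18. Week 14 holds only the twelve 150 mg subjects, mean 0.
- Individual clocks, one early stabiliser only (last change at Week 4): Week 18 has n = 19, mean 0; Week 20 has n = 1, +45; the all-subject mean is 45/20 = +2.25.

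**5. Range for the early-stabiliser share.** The documents do not give this for the present trial. I assume a lower value of 3/43 = 7%, because 40/43 in the earlier US study needed 150 mg (Protocol 4.2.1). I assume an upper value of 47.6%, the Week 26 response rate in the Japanese study (Protocol 1.2). Neither measures the quantity directly.

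**6. Simulation.** 20 subjects, 2,000 trials per scenario. Every platelet curve is non-decreasing, so any fall in the displayed median comes from attendance alone. Baseline values, plateau heights and rise times are assumptions. Chance of a fall of at least 10 x 10^9/L between consecutive visits:

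| Share stabilising early | Individual clocks | Common 4-week grid |
|---|---|---|
| 7% | 52% | 3% |
| 20% | 89% | 11% |
| 40% | 99% | 46% |
| 47.6% | 99% | 66% |

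At a 40% share with individual clocks, mean n at Weeks 14, 16, 18, 20, 22, 24 and 26 was 16.1, 4.2, 16.1, 3.9, 16.1, 3.9 and 20. The mean displayed medians were 28, 98, 29, 97, 30, 97 and 40 x 10^9/L. Up to about Week 14 the early stabilisers are the ones missing, which lowers the median; from Week 16 the off-phase visits hold mainly them, which raises it. On a common grid the effect lies almost entirely at Weeks 6, 10 and 14.

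Restricting the summary to baseline and Weeks 4, 13 and 26 gave n = 20 at each and no fall in any simulated trial.

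**The case against.** A reader of the calendar might infer that Weeks 16, 20 and 24 contain only platelet responders and that every unresponsive 150 mg subject sits in the other set. The documents do not support that. The note under Table 6-3 speaks of 150 mg/day at Week 12. A last step then would make the subject stable at Week 16, with visits at Weeks 20 and 24. A single 2-week delay does the same, and Protocol 6.5.1 allows reductions and stops for adverse events. Nor does Table 8-1 say that each subject's 4-week clock starts at stabilisation.

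The low end of the range also has support. In the earlier US study nearly all subjects needed the top dose, and responses began at about 3 months (Protocol 4.2.2), by which time an uninterrupted non-responder is already at 150 mg. Most subjects would then share one calendar, and an out-of-phase point would rest on one or two people. Against this, Protocol 1.3 reports 50% to 90% higher exposure in Asian patients, so the US share may not carry over.

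The protocol summary lists n among the statistics for the remaining efficacy endpoints, so a careful table reader could see 4 against 16. That helps, but SAP 2.7.2 does not ask for n on the plot, and showing n does not remove the swings. Finally, the display is descriptive, and onset and loss of response have their own Kaplan-Meier analyses. That limits the consequence and leaves the mechanism intact.

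**Conclusion.** The concern holds in a conditional form. Between about Week 6 and Week 24, Week 13 apart, following the plan as written can produce rises or falls in the count summaries and plots that no subject had. The effect is largest with individual 4-week clocks. It is small, and mainly at Weeks 6, 10 and 14, if sites use a common grid and few subjects stabilise early. The attendance pattern follows from the protocol's tables under uninterrupted application; the sizes rest on the assumed share, the assumed curves and the visit alignment.

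It would be wrong to infer that the efficacy result is at risk. The primary endpoint and the Week 13, 26 and 52 response rates are assessed at visits scheduled for everyone on study and are unaffected. This is a worthwhile correction to a descriptive secondary output.

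**What to change.** In SAP 2.1.3 and 2.7.2:

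- Base the count-change table and plot on the visits scheduled for all subjects: baseline and Weeks 1 to 4, 13, 26 and 52.
- Between these, use non-overlapping 4-week windows centred on Weeks 7, 11, 15, 19 and 23, then 29, 33, ... 49.
- Keep values assigned to Weeks 13, 26 and 52 out of the neighbouring windows.
- Apply the SAP's existing closest-to-target and earlier-if-tied rules, show n at each plotted point, and keep nominal-visit values in listings.

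The centres matter. Each row of the calendar above has at least one visit in each pair 6/8, 10/12, 14/16, 18/20 and 22/24, and with these centres each pair falls in one window, 7 days from the centre and 7 days from the edge. Windows centred on Weeks 16, 20 and 24 would instead put Weeks 14, 18 and 22 on the edges. With the 7-day visit tolerance in Protocol section 8 and uniform timing assumed, about a quarter of the subjects on that phase would then have no value in the Week 16 window, and about a quarter none in the Week 20 window. Coverage of the proposed windows was checked by enumeration, not simulation; values lost to transfusion or G-CSF exclusion will still lower n.

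The cost is SAP wording and one programming step, with no new data or visits. The downside is slightly coarser time resolution during dose escalation.
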